### **IFSMT Distal Outcomes.**

#### **Health Status.**

**Exclusivity and Duration of BF** measured by the Ongoing BF Assessment Survey and the BF algorithm.

#### **Quality of Life.**

**PROMIS Global Health.** Measures overall global physical health (function, pain and fatigue) and mental health (quality of life, satisfaction with social activities, and emotional well-being). (See above for scoring).

### **Kaltura modules**

We provide voiced modules as part of our intervention. Please see attachments of breastfeeding intervention, postpartum care attention control, and infant development modules.

**Describe opportunities provided to participants to ask questions** in order for them to make an informed decision regarding participation.

**Participant Recruitment** will use active and passive methods successful in our pilot study with the addition of prenatal recruitment in the clinical sites. Passive methods include advertisements via Facebook pages and Instagram targeting women in Connecticut who intend to BF and flyers posted at Hartford Hospital, UConn Health, Connecticut Women, Infants, and Children prenatal clinics, and in the hospital common areas, given to women who express interest in BF during their prenatal care, and included in hospital discharge educational packets. Women who express interest in the prenatal period will be identified by a "sticky note" in Epic to facilitate recruitment in the postpartum period. Active methods include screening the inpatient unit census 3-7 times per week by our clinical partners for women who meet inclusion/exclusion criteria. Women who agree to speak with a member of the research team about the study will be approached in labor and delivery and in the postpartum unit. In order to ask initial screening questions via UConn Health REDCap, an evaluation of the participant's capacity to

consent will be assessed and a HIPAA consent will be obtained. Women will be asked if they have any questions about the study before and screening, and before and after consent. If eligible, women will be consented in a private setting, by a member of the research team trained in obtaining informed consent. The consent process will be documented at Hartford Hospital and stored with the source documents. Participants will be identified in Epic at both Hartford Hospital and UConn Health to facilitate follow-up at 6 weeks and 6 months.

### **Evaluation of the study**

At 6 weeks, women will be asked in a 10–15-minute audio taped semi-structured interview about their breastfeeding experience. At 6 months, women will be asked in a 10-15-minute audio taped semi-structured interview to review their participation in and the impact of the study (see questionnaire).

### **Data Analysis and Management**

All data will be entered into a password-protected database stored on a firewall-protected server that is maintained by UConn. We will use the existing structure of data management established with our pilot study. The protocols established for trialing and monitoring UConn Health REDCap will be strictly followed. We have designed data collection forms to check for missing data in real-time to avoid incomplete data and routinely monitor data input. Our Project Manager, working with the statisticians, will prepare a weekly data summary, which will be reviewed during weekly team meetings.

**Statistical Analysis Overview.** Prior to undertaking statistical modeling, descriptive statistics will be determined for the study's key independent and dependent variables in order to evaluate the effectiveness of randomization, to check distributional assumptions (such as normality), to identify potential outlying observations, and to obtain preliminary insights into homogeneity versus heterogeneity of variance for outcome measures. Analyses will be conducted using SAS 9.4 and R^194.

**SA1.** Initially, mixed effects linear modeling will be applied to contrast mean levels of pain at the 1-, 2-, and 3-week time points. The analyses will be repeated for a series of pain outcome measures, including BNP intensity, BNP interference, and cumulative BNP. The models will include “main” effects for intervention and time, an interaction between intervention and time, a random effect for “subject”, and the baseline value of the dependent variable as a covariate. Modeling results will be used to test for a time-by-intervention interaction. If the interaction is non-significant, the model will be re-fitted without it and testing will focus on the main effect of intervention. Regression diagnostics will be applied to all models to identify non-normality in residuals and potentially biasing effects of outlying observations. While mixed effects linear models are resistant to the impact of limited amounts of missing data, we will also utilize multiple imputation methods, as described below, to evaluate the sensitivity of model estimates and testing results to missing observations. Following evaluation of intervention effects at the 1-, 2-, and 3-week time points, we will proceed to assess differences in acute and cumulative BNP intensity and interference at 6, 9, 12, 18 and 24 weeks. Additionally, we will investigate whether subject-level “trends” or “growth curves” in pain levels across all eight study time points differ between the intervention and control conditions. If necessary, demographic variables will be included in the regression models both to account for potential confounding effects that might arise via imperfect randomization and to reduce unexplained between-subject variation in outcome variables.

**SA2. H2A.** We will start by investigating the intervention's effect on proportion of exclusive BF after week 6. Initially, the Pearson Chi-square test will be performed to detect the difference between intervention and control groups at 6, 9, 12, 18, and 24 weeks, respectively. Furthermore, a generalized linear mixed model with a logistic link will be applied to analyze the “main effect” of intervention and time, and “interaction effect” of intervention by time. The procedure to fit and re-fit the model will be similar to the approach for pain measures in SA1. The measure for BF self-efficacy, yield scale scores

which range from 14-70. We will treat BF self-efficacy scores as "continuous" variable and follow the approach in SA1 to investigate the intervention effect on BF self-efficacy over time. **H2B.** Subsequently, we will assess intervention effects on maternal well-being - anxiety, depressive symptoms, fatigue, stress, and sleep disturbance over all the time points. Each of these variables' measurement scores will be treated as "continuous" and effects of the *BSM* intervention will be investigated following a similar approach as for the pain measures in SA1. Because these variables are highly interrelated, we will evaluate their response to intervention effects simultaneously. In this approach, differences in the quadrivariate means of these variables between the *BSM* and attention groups will be analyzed using multivariate mixed effects linear modeling in an approach analogous to that for the pain measures in SA1 but with the inclusion of covariances between random intercepts for the anxiety, depressive symptom, fatigue, and sleep disturbance scores at the subject level. Across the modeling procedures related to SA2, regression diagnostics will be applied to investigate suitability of distributional assumptions and potential biasing effects of outliers.

**SA3.** We will model effects of pain sensitivity SNPs on quantitative sensory testing measures, BNP intensity and interference, BF outcomes in SA2, and maternal and pain self-efficacy across all the time points. In addition, we will also assess the effects of individual quantitative sensory testing measures on all the outcome measures aforementioned over time. Analyses will utilize "linear/generalized linear" modeling with univariate and multivariate dependent variables, will account for correct temporal ordering among time varying measures, and will evaluate correlations between measures that jointly vary in time in response to other factors/covariates.

We have planned for attrition rates as high as 25%. However, our goal is to minimize attrition by instituting a participant outreach plan –namely, contacting participants to complete modules, providing monthly updates regarding child development, and encouraging women to remain involved. In statistical analyses, we will follow each model based only on "observed data" with sensitivity analyses in which Markov Chain Monte Carlo multiple imputation is used to assess the possibility and impact of "missing at random" data.

**Statistical analysis of methylation sequencing data.** Post-alignment analysis will be performed by using the MethPipe package (<http://smithlabresearch.org/software/methpipe/>). First, aligned sequences will be converted to MethPipe format using the to-mr command. Methylation levels and coverage for each symmetric CpG site will be calculated. Average CpG methylation levels of annotated genomic regions, i.e., promoters, exons, repeats, CpG islands/shores/shelves (CGI) will be calculated with the MethPipe roimethstat program. Only high-confidence genomic regions with at least 40 CpG observations from reads in the region will be retained for further analyses. Coordinates of promoters (-1000 bp and +100 bp from the transcription start site (TSS)), exons, introns and intergenic regions will be retrieved from Ensembl Regulatory Build (Ensembl release 101) and CGI annotations obtained from the UCSC Table Browser. Tissue-specific enhancer coordinates (+/- 1000 bp from peak) will be retrieved from the Human Encode Project38 (GRCh38/hg38). Hypermethylated regions and hypomethylated regions will be calculated by the hmr command from the MethPipe package. Unsupervised hierarchical clustering of 2 kb tile methylation will be performed using the R hclust command with the "ward" method. Correlation matrix will be calculated by the R corrplot package. Profile plot will be created by the R seqplots package. Gene ontology analysis will be performed by GREAT and DAVID Bioinformatics Resource 6.8. A Univariate ANOVA, followed by post-hoc Tukey HSD will be carried out to compare methylation within promoter region CGI for the six candidate genes (*OXTR*, *COMT*) identified in the preliminary studies. CGI methylation status of each gene will be assessed individually with control for multiple comparisons between conditions maintained, and post-hoc analysis with Tukey HSD will be adjusted to maintain an overall  $\alpha = 0.05$ .

**SA4.** We will model effects of DNA methylation of *OXTR* and promoter regions of *PRLR* haplotypes for different single nucleotides polymorphisms (SNPs) on BNP and maternal perception of lactation insufficiency, BNP intensity and interference, and BF frequency across all the time points. [name], will consult with the Institute for Systems Genomics to assist with statistical data analysis and interpretation of EPIC array raw data.

EPIC array raw data will be imported into the statistical analysis software Partek® Genomics Suite® for normalization, quality control, differential analysis and biological interpretations (gene ontology and/or pathway analysis). Statistical calculations (available within the software) will include Logistic Regression, Chi Square, False Discovery Rate, Fisher Exact, Power Analysis, and ANOVA. We propose to use the significance threshold of  $P < 9 \times 10^{-8}$  to control the false positive rate for EPIC array DNA methylation studies.

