
**SA1:** Examine the effect of the *BSM* intervention on the primary outcome of BNP intensity and interference between the intervention and attention control group controlling for prior BF experience across all data points.

**H1:** The *BSM* group will report significantly lower BNP intensity and interference at 1, 2, and 3 weeks and significantly lower cumulative BNP score over time compared to the AC group.

**SA2:** Examine the effect of the *BSM* intervention on secondary outcomes of BF exclusivity, BF self-efficacy, and maternal well-being.

**H2A:** The *BSM* group will have a higher proportion of women with exclusive BF at 6, 9, 12, 18, and 24 weeks and higher BF self-efficacy at all-time points compared to the attention control group. **H2B:** The *BSM* group will have higher maternal well-being compared to the attention control group at each time point.

**SA3:** Explore (1) the influence of pain sensitivity (quantitative sensory testing, select buccal cell and/or blood samples for pain sensitivity SNPs and in a subsample, DNA methylation of select sensitivity SNPs (40 participants (5 zero and 15 highest pain phenotype per group) on BNP intensity and interference; and (2) BF outcomes in SA2, maternal and pain self-efficacy over time between groups.

**SA4:** Explore (1) the influence of pain sensitivity and lactation (blood samples for pain sensitivity and lactation SNPs [*OXTR* and *PRL*]) on perception of milk supply (BSES and HH lactation scale).

Aligned with the Maternal and Infant Care goals of Healthy People 2020, NINR strategic themes of symptom science and self-management, NICHD optimal infant and maternal health during the fourth trimester, and the CDC *HEAR HER* campaign, the proposed study will address a major barrier to BF initiation and exclusivity by testing the effectiveness of the *BSM* intervention to decrease BNP intensity and interference and increase BF self-efficacy and support maternal well-being. The *BSM* intervention is easily accessible and clinically sustainable allowing for large-scale translation in health care and public health settings.

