### **Enrollment and Randomization**

After informed consent and prior to the start of data collection, the participants will be randomized to the *BSM* intervention or the attention control group and be assigned a unique participant identification number (PID#). The sample size objective for the study is to recruit N = 280 women who will be randomly assigned to the *BSM* or attention control study groups at a 1:1 ratio (140 per group). Random assignment will be performed using an established dynamic minimization algorithm, proposed by Pocock and Simon. The algorithm is implemented thru an R package called "minirand", developed by Jin et al.. The interactive tool is developed as an R shiny app embedded in REDCap. This technique will maintain the 1:1 ratio between participants assigned to the *BSM* and control conditions, but will also ensure that participant characteristics that are known to be predictive of breastfeeding outcomes will each be balanced across the study groups. Those predictive characteristics include: age, race, breastfeeding experience, expected breastfeeding duration, route of delivery, and intent to return to work.

The reason we choose this algorithm is the complexity of the randomization needed for our study. With 280 expected participants and 6 stratifying characteristics, the simple randomization may not yield a balanced arm assignment in every allocation. However, the dynamic feature of our randomization will incorporate both the existing assignments and the imbalance at each level of the stratifying characteristics and assign the next participant to minimize the overall imbalance. With the large number of total enrollments in our study, this also leads to a balanced assignment at each level of the stratifying characteristics. To retain randomness, the probability of making the "best assignment" to minimize imbalance is set to be 90%.

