**Data Collection during Follow up.** After discharge, both groups will receive an encrypted text via UConn Health REDCap with embedded links from Twilio, a cloud communications platform and a back-up archive feature. The follow-up measures at 1, 2, 3, 9, 12, and 18 weeks (Figure 4) include the participants' weekly BNP, pain coping, BF exclusivity, ongoing BF assessment, BF algorithm and maternal assessment of infant BF behaviors, self-efficacy scales (pain, BF, and maternal), maternal well-being assessments, and perceived well-being scales. Completion of the measures will take about 30 minutes. Our statistician team at weekly meetings will identify any missing data to facilitate contact of participants to complete surveys. At 6 and 24 weeks, participants will complete the above measures and repeat quantitative sensory testing and provide buccal cell and/or blood samples for selecting pain sensitivity SNPs and DNA methylation at our clinical locations. Completion of the measures will take about 60 minutes. At Weeks 4, 18 and 20, participants will receive a prompt in their modules to provide their 6 week and 6-month research appointment day and time. If participants do not provide a date and time, research personnel will reach via text (up to three times) to schedule the appointment.

**Blinding.** We will employ blinding whenever possible. The PI and all the research team members involved in data collection or analysis will be blinded to the randomization of the participants, and some of the research team to the group assignment of participants. The statisticians, project manager and graduate assistant will not be blinded to study assignment and ongoing data collection. Research team personnel will follow a strict script to refrain from discussing participant activities, and by using the data management graduate assistant (unblinded) to coordinate assigned condition activities and data collection and analysis. All participants will be assigned a study number, which will be used to track the study measures and buccal cell and/or blood samples. De-identified data with dummy-codes for assigned condition will be entered into the study database to allow blinded data analysis. Blinding was successfully employed during our pilot study.

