***Measures, survey instruments and questionnaires, (including the collection of demographic data).***

**Baseline, Process, and Outcome Measurements (Table 2)**

All of the BNP measures (visual analogue pain scale and Brief Pain Inventory short form), pain coping (Coping Strategies Questionnaire), BF specific factors including demographics, ongoing BF assessment and algorithm, Breastfeeding Self-Efficacy Scale, maternal assessment of infant BF behaviors, maternal well-being symptoms [PROMIS anxiety, sleep, fatigue, perceived stress], Edinburgh Postnatal Depression Scale, perceived well-being [PROMIS global health], pain sensitivity SNPs, and quantitative sensory testing, were successfully collected in the pilot. The effect of the *BSM* intervention on pain self-efficacy, will be measured by the Self-Efficacy for Managing Chronic Illnesses Scale, the Index of Self-Regulation, and on maternal self-efficacy the Karitane Parenting Confidence Scale and Postpartum Bonding Instrument.

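### SA1 is stated as controlling for prior breastfeeding experience, but the SA1 model omits it and leaves all further covariates open

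*Combined protocol and SAP*

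**What the plan says.** The specific aims in the Purpose/Introduction frame SA1 as comparing pain intensity and interference between the intervention and the "attention control group controlling for prior BF experience across all data points".

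Data Analysis and Management, SA1, gives the model: intervention, time, their interaction, a random subject effect, "and the baseline value of the dependent variable as a covariate". One further clause deals with other covariates: "If necessary, demographic variables will be included in the regression models both to account for potential confounding effects that might arise via imperfect randomization". The same clause then gives a second purpose, which concerns precision and not imbalance: "and to reduce unexplained between-subject variation in outcome variables". The SA2 text applies the SA1 approach to BF self-efficacy and to maternal well-being.

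Enrollment and Randomization minimises on six factors: "Those predictive characteristics include: age, race, breastfeeding experience, expected breastfeeding duration, route of delivery, and intent to return to work".

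The Blinding paragraph says: "The statisticians, project manager and graduate assistant will not be blinded to study assignment and ongoing data collection". It also says: "De-identified data with dummy-codes for assigned condition will be entered into the study database to allow blinded data analysis".

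**The concern.** The aim promises adjustment for one named variable, and the model written to serve that aim does not contain it. The only route by which it could enter is a conditional clause that names no variable, sets no threshold and does not say when the choice is made. That clause has two purposes. The first, imbalance, could be judged from baseline data. The second, reducing residual variation, is most naturally judged from the outcomes.

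So a reader cannot tell which covariates the primary result will carry, and the statisticians who fit the model are not blinded. The analysis also does not reflect the factors used in allocation. Where such factors predict the outcome, leaving them out makes the main-effect test conservative and costs some precision.

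**Working it through.** **1. Is prior breastfeeding experience in any SA1 analysis?** SA1 has three parts: weeks 1 to 3, weeks 6 to 24, and growth curves over all follow-up points. None names it. Whether the conditional clause covers it is unclear. IFSMT Context variables lists prior BF experience with breastfeeding and medical history, apart from the demographic items. The Measures section writes more loosely of "BF specific factors including demographics".

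**2. The plan's own sample size.** Inputs from Justification of Sample Size: d = 0.39, two-sided α = 0.05, power 80%, loss up to 25%.
- n per group = 2(1.960 + 0.842)² / 0.39² = 103.2, so 104.
- 104 / 0.75 = 138.7, so 139 per group and 278 in total, against 280 stated.
- With 280 × 0.75 = 210 retained (105 per group), power is 80.7%.

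The figure reproduces. It is a plain two-group calculation with no covariates.

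**3. Closed form, assuming perfect balance.** Let R² be the share of pain variance left after baseline that the six factors explain. The documents give no value, so 0, 5, 10 and 20% are assumed. Put f = √(1 − R²), with d in SD units after baseline. Without the factors, the model reports a standard error of √(2/n) while the true one is f√(2/n).
- Type I error without the factors: 2[1 − Φ(1.960/f)]
- Power without: Φ[(0.39/√(2/n) − 1.960)/f]
- Power with: Φ[0.39/(f√(2/n)) − 1.960]

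For n = 105 per group, 0.39/√(2/105) = 2.826. At R² = 10%, f = 0.949. Type I error is 2[1 − Φ(2.066)] = 3.9%. Power without is Φ(0.866/0.949) = 81.9%, and power with is Φ(2.979 − 1.960) = 84.6%.

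| R² | Type I, without | Power, without | Power, with |
|---|---|---|---|
| 0 | 5.0% | 80.7% | 80.7% |
| 5% | 4.4% | 81.3% | 82.6% |
| 10% | 3.9% | 81.9% | 84.6% |
| 20% | 2.8% | 83.3% | 88.5% |

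**4. Simulation of the actual allocation.** Pocock-Simon minimisation with N = 280 and 90% best assignment (Enrollment and Randomization), 20,000 trials per layout. The documents give no factor categories, so three layouts were assumed, using 6, 9 and 12 degrees of freedom. The test is ANCOVA of each woman's weeks 1 to 3 mean on arm and baseline. With complete data this is the main-effect test of the random-intercept model. Factors are equally weighted and independent of baseline, and attrition is random. Monte Carlo error (95%) is about 0.3 points at 5% and 0.6 points at 80%. Ranges are over layouts; the last column is the share of trials at d = 0.39 in which the two models fall on opposite sides of p = 0.05.

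| Analysed | R² | Type I, without | Power, without | Power, six factors | Opposite conclusions |
|---|---|---|---|---|---|
| 263 (6% lost, as in the pilot) | 0 | 4.8–5.1% | 88.2% | 88.0–88.2% | 0.8–1.1% |
| | 5% | 4.3–4.6% | 88.6–88.8% | 89.6–89.7% | 1.5–1.9% |
| | 10% | 3.8–4.1% | 89.2–89.4% | 91.1–91.2% | 2.1–2.6% |
| | 20% | 2.9–3.2% | 90.3–90.5% | 93.8–94.0% | 3.6–3.9% |
| 210 (25% lost) | 0 | 4.7–5.1% | 79.9–80.3% | 79.4–79.6% | 2.2–3.0% |
| | 5% | 4.4–4.7% | 80.3–80.7% | 81.3–81.6% | 3.6–4.0% |
| | 10% | 4.0–4.3% | 80.7–81.0% | 83.5–83.6% | 4.8–5.0% |
| | 20% | 3.3–3.5% | 81.6–82.0% | 87.6–87.8% | 7.3–7.5% |

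Type I error with the six factors included was 4.7 to 5.2%.

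**5. Prior breastfeeding experience alone.** If it carries one sixth of R², power with 210 analysed is 80.5–80.7, 81.3–81.4 and 82.6–82.9% at R² of 5, 10 and 20%. Matched by layout, the gain over the listed model is 0 to about 1.2 points.

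**6. Interaction test.** Time-constant covariates do not enter within-woman contrasts. In a random-intercept fit to one complete simulated dataset, interaction estimates and standard errors were identical with and without them.

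**The case against.** The strongest reply is that the conflict may be verbal. Minimisation balances prior breastfeeding experience, and the protocol elsewhere uses the language of control for a design feature, its attention group. The conditional clause might also cover the variable, since the relevant paragraph of IFSMT Context variables sits under a heading ending in demographics. A descriptive check of randomisation is planned before modelling, which offers a natural point for judging imbalance. The Blinding paragraph is itself mixed: it also says that team members involved in analysis are blinded.

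These points soften the concern but do not remove it. An aim worded to apply at every data point reads most naturally as analysis, and balance at allocation does not put the factor in the model. A conditional clause cannot deliver an unconditional adjustment. The descriptive check is not tied to covariate choice, and it could not serve the clause's variance purpose.

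Three objections on scope and size do stand. Only prior breastfeeding experience is promised, and only for SA1; the other five factors and the SA2 models are a matter of good practice. Most of the figures above therefore concern more than the promised adjustment. And the 25% loss is a 24-week figure, so the 210 rows are pessimistic for a weeks 1 to 3 test. Some opposite conclusions also occur when the factors predict nothing; net of that, the rate with 263 analysed is 0.7 to 2.8 points.

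**Conclusion.** The concern holds. The listed SA1 model omits the one covariate its aim names, and the rule for any other covariate has no list, criterion or timing. The continuous SA2 models inherit that open rule.

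The statistical cost is modest and in the safe direction: a somewhat conservative main-effect test, and with 263 analysed a power shortfall of about 1 to 3.5 points against the six-factor model. The stated power and N stand, confounding is not the issue, and the interaction test is unaffected with complete data.

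The sizes rest on assumed R² values, factor categories and equal weights. The protocol describes the factors as predictors of breastfeeding results and gives no R² for pain. The inconsistency and the open covariate rule do not depend on those assumptions. This should be corrected, but it does not threaten the trial's validity.

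**What to change.** Reconcile the SA1 aim with the SA1 model. Name prior breastfeeding experience as a fixed covariate in all SA1 models, preferably with the other five minimisation factors and their categories. Do the same in the continuous SA2 models (BF self-efficacy and maternal well-being). Replace the conditional clause with a rule that any other covariate enters only in a labelled sensitivity analysis. Adding the same factors to the logistic mixed model for exclusive breastfeeding is optional, and the chi-square tests need no change.

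This takes one or two sentences and no new data, because the six factors are already entered for the allocation tool. Six factors use 6 to 12 degrees of freedom if each has two or three levels. If none is prognostic, the simulated loss of power is at most 0.2 points with 263 analysed and under 1 point with 210. Prior breastfeeding experience alone uses 1 or 2 degrees of freedom and costs 0.2 points or less.
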